ANTICOAGULANT DOSAGE AND ADMINISTRATION	
Pre-procedure: Unfractionated heparin will be administered IV to prolong the aPTT pre-procedure (suggested range 60-80 seconds).
 
Note: Use of enoxaparin (Lovenox®) is permitted pre-procedure for the treatment of PE. If Lovenox is given, then catheter directed thrombolysis procedure is to start no sooner than 12 hours after the last Lovenox dose was administered.
 
Procedure: Heparin infusion will be discontinued upon arrival in the IR/Cath lab. ACT will be monitored in IR/Cath Lab and heparin boluses administered to achieve ACT \geq 200 seconds.
 
During r-tPA Infusion: Heparin infusion will be restarted post-procedure and administered through the side arm of each sheath to prolong the aPTT (suggested range 40-60 seconds).
 
Post r-tPA Infusion: Upon completion of r-tPA infusion, maintain patency through the BEC by replacing r-tPA with heparinized saline TKO using the infusion pump. Starting 45 minutes (\pm 15 minutes) after the r-tPA completion, administer Lovenox 1mg/kg sub-Q every 12 hours (\pm30 minutes) through the completion of the 48-hour CTA.

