7.1.4 Anticoagulation

Unfractionated heparin is required to be used for anticoagulation and is to be started pre-procedure by intravenous administration to prolong the aPTT (suggested range is 60-80 seconds) unless the patient has received Lovenox.

The institution is to follow the standard of care for the administration of heparin and the monitoring of aPTT in addition to the aPTTs measured at certain time points required by this protocol. Stop the heparin administration at the completion of the r-tPA infusion. The final aPTT should be measured according to standard of care.

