- k. Ensure the BEC(s) are adequately flushed. Attach the flushed pressure transducer tubing to the wire lumen of the BEC(s). Measure the systolic PA, diastolic PA, and mean PA pressures in each PA with a pulmonary embolism from the tip of the BEC through the guidewire lumen at the back of the BEC handle. Print the PA waveform tracings and mark the tracings where the systolic PA, diastolic PA, and mean PA pressures are interpreted and documented.
- l. If the waveform is damped, adequately flush the wire lumen. If the waveform is still damped after it is flushed, print the damped waveform on paper, and retain the waveform with the source documentation for this study. Measure the systolic PA, diastolic PA, and mean PA pressures in each PA with a pulmonary embolism on the tracing. If the waveform becomes phasic prior to leaving the lab, print the waveform, mark on the waveform where the systolic PA, diastolic PA, and mean PA pressures are interpreted and the time the waveform became phasic. Retain the printout with the source documentation for this study.

9.3.2 Part 2 – r-tPA Infusion and Anticoagulation – Prior to Departing the IR suite/Cath lab r-tPA Infusion

Upon completion of the Pulse Sprays, with the basket re-expanded and catheter securely in place, begin r-tPA solution infusion(s), as soon as possible (immediately following the pulse sprays).

1. **For unilateral PE:** The total r-tPA is 10mg at 1.27mg/hr. Using an IV pump at 95cc/hour, infuse the 750cc of 0.9% NaCl with the 10mg r-tPA at 1.27mg/hr until infusion is complete (approximately 8 hours).
2. **For bilateral PE:** The total r-tPA dose is 10mg at 1.30mg/hr. Using two (2) IV pumps at 65cc/hour, infuse the 500cc of 0.9% NaCl x 2 simultaneously with the 5mg r-tPA at 0.65mg/hr for each PE for a total of 1.3mg/hour until complete (approximately 8 hours).
3. **Anticoagulation:** Re-start low dose heparin infusion into each sheath to prolong the aPTT (suggested range 40 to 60 seconds) prior to leaving the

IR suite/Cath lab to maintain therapeutic dose through completion of the 48-hour CT scan.

The institution is to follow the standard of care for the administration of heparin and the monitoring of aPTT in addition to the aPTTs measured at certain time points required by this protocol.

4. **Maintaining Patency Through the Central Lumen of the BEC(s):**

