10.0 POST-PROCEDURE PATIENT MANAGEMENT AND TESTS

The study subject will be admitted to the intensive care unit (ICU) where nursing staff are experienced in the care of patients treated for pulmonary embolisms.

10.1 r-TPA Infusion – Intensive Care Unit

1. **r-tPA Infusion:** Maintain the r-tPA Infusion through the infusion line on the side of the handle of the BEC in the ICU for approximately eight (8) hours from start of the infusion in the IR suite/Cath lab. The infusion should run at the rate prescribed in this protocol until the infusion is complete.
 - a. **Unilateral PE:** Infusion rate is to be maintained at 95cc/hour through the BEC, for a total of 1.27mg/hour infusing into the patient over approximately eight (8) hours. (95cc/hr= 1.27mg/hour x 1 infusion x approximately 8 hours = 10mg total). Infuse the r-tPA mixture until the infusion is complete.
 - b. **Bilateral PE:** Infusion rate is to be maintained at 0.65mg/hour through each catheter, for a total of 1.3mg/hour infusing into the patient (0.65mg/hour through each BEC). This is a rate of 65cc/hour per infusion for a total of 130cc/hour total infusing through two catheters into the patient. Infuse the r-tPA mixture until the infusion is complete
2. **Laboratory Tests:** Four (4) hours (\pm 1 hour) after initiation of heparin infusion started in the IR suite/Cath lab measure:
 - a. CBC
 - b. aPTT
3. **Hemodynamic Readings:** Record the following pressures in the ICU beginning with the 1st reading two (2) hours (\pm 30 minutes) after the initiation of the r-tPA infusion and then every thirty (30) minutes (\pm 15 minutes) thereafter through the central lumen of the BEC. If a waveform, or both waveforms (if bilateral) appear damped, verify each BEC pressure transducer is set up properly when study subject arrives in ICU. If the waveform continues to be damped, document the date and time when the waveform becomes phasic and print the waveform from the monitor. Mark on the waveform where the systolic PA, diastolic PA, and mean PA pressures are read and retain with the source documentation for this study. Please note that when the waveform becomes phasic, it must be documented even if it outside of the “every 30 minutes” scheduled readings. This is so the length of time from the 1st pulse spray (in the Cath/IR lab) to when the

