clot dissolves in each PA with a pulmonary embolism will be known. Please note that printouts are not required for every reading, only when the damped waveform becomes phasic, if damped when subject arrives in the ICU. These readings are required through the completion of r-tPA infusion:

- a. PAS / PAD / PA Mean Pressures
- b. SpO₂ – Arterial Oxygen Saturation (pulse oximeter O₂ saturation)

4. **Mixed Venous Oxygen Saturation (SvO₂):** Record every two (2) hours (± 30 minutes) in the ICU starting after the initiation of the r-tPA infusion. These readings are required through the completion of r-tPA infusion:
 - a. SvO₂ – Mixed Venous Oxygen Saturations (Sample is from tip of the BEC, drawn from the central lumen of the BEC at the end of the handle. If bilateral, either BEC is acceptable for drawing the SvO₂.)
5. **Anticoagulation – Intensive Care Unit During r-tPA Infusion:** Heparin drip should be administered until the r-tPA infusion is complete (approximately 8 hours).
6. **Anti-coagulation Immediately Post-rtPA Infusion:** Once the r-tPA infusion is complete, turn off the heparin gtt. Starting 45 minutes (± 15 minutes) after the r-tPA completion, administer Lovenox 1mg/kg sub-Q every 12 hours (± 30 minutes) through the completion of the 48-hour CTA.
7. **Physical Exam:** A physical exam is required to be performed at the completion of the r-tPA infusion.
8. **Stopping r-tPA Infusion in ICU at the End of 8 Hours:** Upon completion of r-tPA infusion, maintain patency through the BEC by replacing r-tPA with heparinized saline using the infusion pump, at TKO, and transport to IR suite/Cath lab to remove BEC. Heparinized saline should infuse via infusion pump through the basket infusion port until subject arrives at the IR suite/Cath lab for catheter removal.

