21.0 APPENDICES

APPENDIX 21.1 REQUIRED STUDY PROCEDURES

Test	Pre-Procedure	Procedure	Post-Procedure	End of Infusion	24 Hrs Post-r-tPA Completion	48 Hrs Post-r-tPA Completion	72 Hrs Post- r-tPA Initiated	Before Discharge	30-day Follow-up
Visit Window	≤ 48 Hrs of procedure			+8 Hrs	± 8 Hrs	± 6 Hrs	-4 / +12 Hrs	-8 Hrs	± 7 Days
Informed Consent	X								
Demographics and Medical History	X								
Physical Examination	X			X	X			X	X
12 Lead ECG	X							X	
CBC, INR ¹	X		X ²		X				
aPTT	X ²		X	X					
Fibrinogen ³	X			X					
CMP	X								
BMP					X				
Cardiac Biomarkers: Troponin I, BNP	X				X				
Lower Extremity Venous DUS	X								
Contrast Enhanced CTA of the Chest	X						X		
RV/LV Diameter Ratio with each CTA	X						X		
Echocardiogram	X				X				
RV/LV Diameter Ratio with each Echocardiogram	X				X				
Eligibility Criteria	X	X							
Anticoagulation ³ (Heparin, Lovenox)	X	X	X	X	X	X			
IR / Cath Lab: Invasive Hemodynamic Data / ACT ⁴		X		X					
IR / Cath Lab: r-tPA Pulse Sprays Administration		X							
Bashir™ Endovascular Catheter(s) and r-tPA Use ⁵		X	X	X					
ICU: PAS / PAD / Mean PA q 30 Min via BEC			X	X					
ICU: Mixed venous SvO ₂ q2 Hours via BEC			X	X					
r-tPA Infusion		X	X						
Medications	X	X	X	X	X	X	X	X	X
AEs / SAEs		X	X	X	X	X	X	X	X
Contrast Enhanced CTs to Core Lab	X					X			
Echocardiograms to Core Lab	X				X				

¹INR is only required at baseline for patients on Coumadin (warfarin) and must be ≤ 1.5 prior to enrollment. If patient is eligible for the study, Coumadin will be discontinued temporarily for study purposes.

[figure not shown]
²Pre-procedure suggested aPTT 60-80s. Suggested aPTT during r-tPA administration is 40-60s. Check aPTT and CBC 4 hr (± 1 hr) after heparin is restarted in the IR suite/Cath lab (suggested range 60-80s).

[figure not shown]
³Unfractionated Heparin will be infused IV pre-procedure or Lovenox. Stop Heparin prior to start of procedure. Restart Heparin post procedure with r-tPA infusion. Fibrinogen to be drawn at time of BEC removal in IR suite/Cath lab. Heparin infusion will continue until the completion of the r-tPA infusion. Lovenox 1mg/kg Sub-Q will be started 45 minutes (± 15 minutes) from the completion of the r-tPA infusion and given q12hrs (± 30 min).

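### Appendix 21.1 footnote 2 suggests an aPTT of 60-80 s for the 4-hour heparin check, which falls during r-tPA, where the rest of the protocol suggests 40-60 s

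*Combined protocol and SAP*

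**What the plan says.** The protocol gives two suggested aPTT ranges for unfractionated heparin, one for each phase of treatment.

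- **Before the procedure or before r-tPA: 60-80 s.** Section 7.1.4 has heparin "started pre-procedure by intravenous administration to prolong the aPTT (suggested range is 60-80 seconds"). The synopsis, section 7.1.1 item 2 and the first sentence of footnote 2 in Appendix 21.1 agree.
- **While r-tPA runs: 40-60 s.** In the synopsis, heparin during the infusion is "administered through the side arm of each sheath to prolong the aPTT (suggested range 40-60 seconds"). Section 9.3.2 item 3 reads "Re-start low dose heparin infusion into each sheath to prolong the aPTT (suggested range 40 to 60 seconds"). The second sentence of footnote 2 reads "Suggested aPTT during r-tPA administration is 40-60s".

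The last sentence of footnote 2 then places the aPTT and CBC at 4 hours (±1 hour) "after heparin is restarted in the IR suite/Cath lab (suggested range 60-80s").

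Section 10.1 item 2 orders the same test, 4 hours (±1 hour) "after initiation of heparin infusion started in the IR suite/Cath lab measure", but gives no target range. On timing, footnote 3 says "Restart Heparin post procedure with r-tPA infusion", and section 10.1 item 6 says "Once the r-tPA infusion is complete, turn off the heparin gtt". Lovenox follows.

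**The concern.** Footnote 2 contradicts itself in consecutive sentences, and its last sentence contradicts the synopsis and section 9.3.2. It is also the only place that ties a range to this particular measurement, because section 10.1 item 2 is silent. An ICU nurse or coordinator working from the schedule of procedures would find 60-80 s next to the 4-hour result.

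The error pushes one way. A result the main text accepts looks low and invites a heparin increase; a result above the intended range looks acceptable and is left alone. Either way the subject gets more heparin than intended while a thrombolytic is running. This happens inside the 72-hour window of the primary safety endpoint, ISTH major bleeding (section 6.2.1). With at most ten subjects, one major bleed moves the observed rate by 1/10, or 10 percentage points, so an avoidable contributor would also make the result harder to interpret.

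**Working it through.** The question is whether the 4-hour check falls during r-tPA, and whether any other phase of heparin could carry the 60-80 s range.

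**Inputs**

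- Unilateral PE: 10 mg in 750 cc at 95 cc/h (section 9.3.2 item 1, Table 2).
- Bilateral PE: 5 mg in 500 cc at 65 cc/h through each of two catheters, 10 mg in all (section 9.3.2 item 2, Table 2).
- Check: 4 ± 1 h after heparin restart, so 3 to 5 h (section 10.1 item 2; Appendix 21.1 footnote 2).
- Delay *d* from r-tPA start to heparin restart: not given. Section 9.2 step 6 starts r-tPA before the catheter enters the sheath, and section 9.3.2 item 3 restarts heparin before the patient leaves the lab, so *d* may exceed zero. I take 0 to 2 h as an assumption.

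**Step 1: infusion length (volume / rate)**

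- Unilateral: 750/95 = 7.89 h, at 10/7.89 = 1.27 mg/h.
- Bilateral: 500/65 = 7.69 h, at 2 × 0.65 = 1.30 mg/h in total.

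Both reproduce the protocol's figure of approximately 8 hours.

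**Step 2: is the check inside the infusion?**

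The latest check, at 5 h, is inside if *d* is below the infusion length minus 5:

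- bilateral: 7.69 − 5 = 2.69 h
- unilateral: 7.89 − 5 = 2.89 h

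The nominal 4 h check is inside if *d* is below 7.69 − 4 = 3.69 h (bilateral) or 7.89 − 4 = 3.89 h (unilateral).

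**Step 3: how much r-tPA is still to come at the check?**

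Time remaining = infusion length − (*d* + check time); dose remaining = time remaining × rate. The low end uses bilateral PE and the 5 h check; the high end uses unilateral PE and the 3 h check.

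| *d* (assumed) | Infusion time left | r-tPA left of 10 mg |
|---|---|---|
| 0 h | 2.69-4.89 h | 3.5-6.2 mg |
| 1 h | 1.69-3.89 h | 2.2-4.9 mg |
| 2 h | 0.69-2.89 h | 0.9-3.7 mg |

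Pump pauses for the pulse sprays are ignored; they would only lengthen the infusion.

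**Step 4: could 60-80 s belong to a later heparin phase?**

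No. Footnote 3 and section 10.1 item 6 end heparin when r-tPA ends. Section 9.3.2 item 3 does still say that heparin runs to the 48-hour CT, which conflicts with section 10.1 item 6 and is a separate matter. Even on that wording, the 3 to 5 h check falls during r-tPA for the delays above, and that same item suggests 40-60 s.

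**Step 5: overlap of the two ranges**

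The upper limit of 40-60 s is the lower limit of 60-80 s, so they share only 60 s.

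| 4-hour aPTT | Main text (40-60 s) | Footnote 2, last sentence (60-80 s) |
|---|---|---|
| 40-59 s | in range | low |
| 60 s | in range | in range |
| 61-80 s | high | in range |

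**The case against.** The strongest reply is that no binding instruction is broken. Every range is only suggested; sections 7.1.1, 7.1.4 and 9.3.2 leave heparin and additional aPTT monitoring to institutional standard of care; and no endpoint or stopping rule uses an aPTT taken during r-tPA. The correct range sits in the sentence before the wrong one, so a careful reader could spot the slip. The analysis is descriptive and unpowered (section 16.2), so no calculation changes. All of this is true, and it limits the weight of the point. It does not remove it: the protocol chose to suggest a lower range during lysis and then suggests a higher one for the aPTT it schedules mid-infusion.

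Three smaller points deserve mention.

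- Section 7.1.5 and section 9.3.2 item 3 describe the restarted heparin as maintaining a therapeutic dose, and section 9.3.2 item 3 also calls it low dose. That wording is loose, but it supplies no competing number; where the main text gives a range during r-tPA, it is 40-60 s.
- In the schedule as extracted, the footnote mark sits on the post-procedure CBC cell and not on the post-procedure aPTT cell. This may come from reading the PDF, and the footnote names the aPTT in any case.
- The milligrams remaining show that r-tPA is still running at the check. They do not measure how far heparin dosing, or bleeding, would change.

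**Conclusion.** The concern holds, and the last range in footnote 2 is wrong as written. It should be fixed, because it is an incorrect target in the required-procedures table and errs toward more heparin during thrombolysis.

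That the whole check window lies within the infusion rests on heparin restarting less than 2.69 h (bilateral) or 2.89 h (unilateral) after r-tPA starts. Over an assumed delay of 0 to 2 h, 0.7 to 4.9 h and 0.9 to 6.2 mg of the infusion remain at the check. That the 60-80 s figure was carried over from the pre-procedure range is an inference from where else it appears, and the conclusion does not depend on it. The size of any effect on bleeding cannot be derived from the documents.

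**What to change.** Change the last range in footnote 2 of Appendix 21.1 to 40-60 s, state the same range beside the 4-hour aPTT in section 10.1 item 2, and notify the sites (at most five). The footnote correction alone removes the contradiction; the addition to section 10.1 puts the target where the test is ordered. Keep the ranges as suggestions under institutional standard of care, and accept that some variation between sites will remain.

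The cost is two short text corrections in the next amendment and a note to sites. No new test is needed, since the 4-hour aPTT is already drawn, and the sample size, endpoints and analysis are unchanged.

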7.1.5 Patients Receiving Lovenox for Treatment of Pulmonary Embolism

Lovenox: Use of Lovenox is permitted pre-procedure for the treatment of PE if it is the standard of care. If Lovenox is administered to a potential study subject, then catheter directed thrombolysis procedure is to start no sooner than 12 hours from the last Lovenox dose.

During the CDT procedure in the IR suite/Cath lab ACTs will be checked and heparin bolus given to achieve ACT ≥ 200 seconds.

After completion of the CDT procedure, a heparin drip will be started prior to leaving the IR suite/Cath lab to maintain therapeutic dose through completion of the r-tPA infusion.

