9.1 Baseline Readings - Summary of Procedure Steps

1. It is recommended that the patient's blood pressure is under control prior to the investigational procedure, with BP < 180/110 mmHg prior to PMCDT.
2. Discontinue the peripheral IV heparin drip infusions.
3. Obtain venous access using ultrasound guidance and Micropuncture needle. Ultrasound guidance and use of Micropuncture needle is mandatory for both CFV and IJ access.
4. Place 7F sheath(s) or larger in the RCFV or access point of choice (LCFV or IJ).
5. Check ACT - If ACT < 200 seconds, administer additional heparin bolus until ACT is documented to be \geq 200 seconds.
6. Using a .035in. exchange length wire, insert the wire into a sheath and advance it up to the right atrium.

7. Insert the Swan-Ganz or angled pigtail catheter over the wire and advance it up to the right atrium.
8. Remove the guide wire.
9. Float the Swan-Ganz catheter or angled pigtail, and record baseline hemodynamic data in section 8.2.
10. Insert the exchange length STORQ™ (Cordis) guide wire, or equivalent, into the Swan-Ganz or angled pigtail catheter. Remove the Swan-Ganz or angled pigtail catheter.
11. Exchange the Swan-Ganz Catheter, or angled pigtail, for a long 7F sheath (or larger) which is placed into the PA where the thrombus is located.
12. Remove the guidewire and the dilator carefully from the PA making sure that the sheath does not jump forward.

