10.2 Return to The IR suite/Cath lab at The Completion of Infusion

At the end of the infusion the patient returns to the IR suite/Cath lab within eight (8) hours (+8 hours) of the completion of the r-tPA infusion for removal of the BEC(s) and final hemodynamic measurements.

1. Under fluoroscopy, collapse the basket(s) of the BEC.
2. Remove the BEC by pulling the catheter(s) carefully into the sheath(s) and then removing them from the body.
3. Back bleed or aspirate the sheath(s) and flush with heparinized saline to prevent clot formation.
4. **Catheter for Hemodynamic Readings and Blood Draws:** Insert a Swan-Ganz or angled pigtail catheter through the sheath and record the following.
 - a. **Hemodynamic Readings**
 - i. SvO₂ – Mixed Venous Oxygen Saturations
 - ii. SpO₂ – Arterial Oxygen Saturation (pulse oximeter)
 - iii. PA Pressures: PAS / PAD / PA Mean

- iv. CO – Modified Fick calculation (Refer to Terms and Definitions for required calculation)
- v. CI – Calculation

b. Fibrinogen – To be drawn at the time of the device removal in the IR suite/Cath lab. *The assay method must be recorded (e.g. Clauss, PT-derived fibrinogen assay, immunological, gravimetric, other)*

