10.7 Tests Required Just Prior to Hospital Discharge

10.7.1 Assessments

1. **Physical Examination** – The physician will perform a physical examination within eight (8) hours (-8 Hours) of discharge.
2. **AE/SAEs** – Adverse events will be monitored and reported on the CRF post-procedure through discharge.
3. **12-Lead Electrocardiogram** – To be done prior to and no greater than within eight (8) hours (-8 Hours) prior to discharge.

11.0 30-DAY FOLLOW-UP VISIT POST PROCEDURE

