⁴Required: PAS, PAD, PA Mean, CO, CI, SpO₂, SvO₂ / ACT - in IR/Cath lab at baseline (print waveforms) and post-infusion in the IR suite/Cath Lab. Swan-Ganz or angled pigtail may be used. CO= Modified Fick calculation. ACT will be done to achieve (and document) an ACT ≥ 200 seconds.

⁵IV solution must be mixed according to protocol and infuse at the prescribed rate into target PA, or both PAs if bilateral PE. Infusion is to be administered at the rate prescribed in this protocol, which is a duration of approximately 8 hours. Once the r-tPA infusion is complete, heparinized saline must infuse TKO using the infusion pump until BEC removal.

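### Section 9.3.2 item 3 runs heparin on to the 48-hour CT, while the rest of the protocol stops it when r-tPA ends and gives Lovenox instead

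*Combined protocol and SAP*

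**What the plan says.** **Heparin.** Section 9.3.2 item 3 belongs to the steps done before the patient leaves the IR suite or cath lab. It restarts a heparin infusion into each sheath (suggested aPTT 40-60 seconds) and makes the 48-hour CT the point to which the therapeutic dose is kept up.

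Five other places end heparin with the r-tPA infusion:
- 7.1.1 item 2: standard-of-care heparin up to the end of r-tPA.
- 7.1.4: heparin stopped at the end of r-tPA.
- 7.1.5, for patients who had Lovenox before the procedure: a drip started before leaving the lab and kept therapeutic until r-tPA ends.
- 10.1 items 5 and 6: a drip until r-tPA ends, then turned off.
- Appendix 21.1 footnote 3: heparin until r-tPA ends.

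The synopsis, 10.1 item 6, 10.4.1, 10.5.1 and 10.5.2 give the time from there to the 48-hour CTA to Lovenox 1 mg/kg. By the synopsis and 10.1 item 6 it starts 45 ± 15 minutes after r-tPA ends and is repeated every 12 hours ± 30 minutes.

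**ACT.** Footnote 4 of Appendix 21.1 requires hemodynamic readings and ACT "in IR/Cath lab at baseline (print waveforms) and post-infusion in the IR suite/Cath Lab", and adds "ACT will be done to achieve (and document) an ACT ≥ 200 seconds" with no visit attached. Its schedule row is marked at Procedure and at End of Infusion. Section 10.2 item 4, which covers the return to the lab, says "Insert a Swan-Ganz or angled pigtail catheter through the sheath and record the following". The list that follows has SvO2, SpO2, PA pressures, CO, CI and fibrinogen, but no ACT. Elsewhere the target of at least 200 seconds belongs to the index procedure: the synopsis under its Procedure heading ("ACT will be monitored in IR/Cath Lab and heparin boluses administered to achieve ACT"), 7.1.5 ("During the CDT procedure in the IR suite/Cath lab ACTs will be checked and heparin bolus given") and 9.1 step 5 ("If ACT < 200 seconds, administer additional heparin bolus until ACT is documented").

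**The concern.** Section 9.3.2 is in use at the moment heparin is restarted, so the stop time it gives could be carried into the order. That stop time runs through the whole Lovenox period. Taken at its word, it means a heparin infusion together with treatment-dose Lovenox in patients who have just had a lytic.

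Major bleeding within 72 hours of starting r-tPA is the primary safety endpoint. With up to 10 subjects at up to five sites, one event is 1/10 = 10% of the sample. If that bleed followed dual anticoagulation at a site that had followed 9.3.2, nobody could say whether the device, the r-tPA dose or the protocol's own wording was responsible. Sites following different sections would also give different anticoagulation inside the endpoint window.

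The ACT wording is a smaller matter. A site cannot tell whether a missing ACT at the return, or one below 200 seconds, counts as a protocol deviation.

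**Working it through.** The conflict itself is a matter of text. The protocol gives no figure for any overlap, so the size below is timing arithmetic from its own windows.

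**Inputs**
- Infusion volumes and rates (Table 2): unilateral 750 cc at 95 cc/hr; bilateral 500 cc at 65 cc/hr per catheter.
- First Lovenox dose (10.1 item 6): 45 ± 15 min, or 0.5-1.0 h after r-tPA ends. Later doses every 12 h ± 30 min.
- CTA (10.4.1): 48 ± 6 h, or 42-54 h after r-tPA ends.
- Return to the lab (10.2): "within eight (8) hours (+8 hours) of the completion of the r-tPA infusion".
- Sheath removal (10.5.3): at the treating investigator's discretion, but as soon as possible once the catheter is out.
- Primary safety window (6.2.1): 72 h from the start of r-tPA.

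**Step 1. Length of infusion** = volume / rate.
- Unilateral: 750/95 = 7.89 h. Bilateral: 500/65 = 7.69 h. Pulse-spray pauses are ignored.

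**Step 2. Overlap if 9.3.2 item 3 is followed and the sheaths stay in** = CTA time minus first Lovenox dose.
- Shortest: 42 − 1.0 = 41.0 h. Nominal: 48 − 0.75 = 47.25 h. Longest: 54 − 0.5 = 53.5 h.
- Lovenox doses by the CTA: 4 at 42 h and 5 at 54 h. Both dose-timing extremes give the same counts. Starting at 0.5 h and repeating every 11.5 h, doses fall at 0.5, 12.0, 23.5, 35.0 and 46.5 h. Starting at 1.0 h and repeating every 12.5 h, they fall at 1.0, 13.5, 26.0, 38.5 and 51.0 h.
- Latest end, counted from the start of r-tPA: 7.89 + 54 = 61.89 h, so all of it lies inside the 72 h.

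**Step 3. Overlap if heparin ends with sheath removal at the return.** Item 3 gives the heparin through the sheaths, so it cannot outlast them by that route.
- If the bracketed 8 hours only restates the limit, the return falls 0-8 h after r-tPA ends. Overlap: 0 to 8 − 0.5 = 7.5 h. The second Lovenox dose comes at 0.5 + 11.5 = 12.0 h at the earliest, so at most one dose is involved.
- If the 8 hours is additive, the return falls 0-16 h after r-tPA ends. Overlap: up to 16 − 0.5 = 15.5 h.
- The first reading is the better supported. The Appendix gives the End of Infusion window as +8 hours, and 10.7.1 uses the same bracket style to restate a limit ("within eight (8) hours (-8 Hours) of discharge").

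**Step 4. Overlap if 10.1 item 6 is followed.** Heparin goes off when r-tPA ends and Lovenox starts 0.5-1.0 h later. Overlap: 0 h.

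**Step 5. ACT wording.** The synopsis, 7.1.5 and 9.1 step 5 tie the target to the index procedure. Sections 10.1 and 10.2 do not mention ACT. What is left is an ACT entry at End of Infusion with no counterpart in 10.2, and a target sentence that names no visit.

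**The case against.** The best reply is that one stray phrase stands against five consistent instructions. Section 10.1 item 6 is the specific order for the moment r-tPA ends, and the same item starts Lovenox. A site reading the whole protocol would turn heparin off. Sheath removal gives a second limit even if it did not. In addition, 7.1.5 is headed for patients who had Lovenox beforehand, so its closely similar sentence is weaker support for all subjects. Most of this stands as an argument about size: the long overlap is not what one should expect. It does not remove the conflict. Both instructions are current text, no reading reconciles them, and 10.5.3 leaves the time of sheath removal to the investigator.

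On footnote 4, the row combines hemodynamics and ACT, so the End of Infusion mark may be meant for the hemodynamics. The target sentence also resembles 9.1 step 5. That benign reading of the target is plausible. However, the footnote itself lists ACT among the post-infusion requirements, so the mismatch with 10.2 remains.

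A reader might infer two stronger things.
- That the protocol calls for a heparin bolus at the return, on top of Lovenox. It does not. No section orders a bolus there, and the number of patients who would receive one may be zero.
- That subjects would routinely receive about two days of heparin with Lovenox. That needs 10.1 item 6 to be ignored and the sheaths to stay in until the CTA.

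**Conclusion.** Section 9.3.2 item 3 is wrong as written and should be corrected. It contradicts 7.1.1, 7.1.4, 7.1.5, 10.1 items 5-6 and footnote 3, and its heparin period overlaps the Lovenox period. This rests on current text alone and not on the version history.

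The size depends on what a site does:
- Follows 10.1 item 6: no overlap.
- Misses 10.1 item 6 but removes the sheaths at the return: about 0-7.5 h, or up to 15.5 h on the additive reading.
- Leaves the sheaths in until the CTA: 41.0-53.5 h and 4-5 Lovenox doses.

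The first two are the realistic cases. The figures assume infusions run at the stated rate without interruption and, in the second case, that the sheaths come out at the return visit. The point bears on patient safety and on how bleeding in the primary window is interpreted. It changes no sample size or error rate, because the study is descriptive.

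The ACT mismatch between footnote 4 and 10.2 is a minor wording note and would not carry the point alone.

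**What to change.** 1. In 9.3.2 item 3, replace the 48-hour CT as the heparin stop point with the end of the r-tPA infusion. The other five places need no change.
2. In Appendix 21.1 footnote 4, state that the ACT target of at least 200 seconds applies to the index procedure only, as in 9.1 step 5.
3. Make the End of Infusion ACT entry agree with 10.2. Either remove it from the footnote and the schedule row, or add ACT to the 10.2 item 4 list as a measurement with no target.

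The cost is one phrase, one footnote sentence, and one table label or list item. No visit or endpoint changes, and no test is added beyond what footnote 4 already lists.
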